8.3.1.1 Change from Study 8HA01EXT Baseline

Hematology and chemistry results at baseline and post baseline visits, along with change from baseline, will be summarized with descriptive statistics for Safety Analysis Set.

8.3.1.2 Shifts

Each subject’s laboratory values will be classified according to whether the test result is “low” (below the lower limit of normal [LLN]), “normal” (within the normal range), “high” (above the upper limit of normal [ULN]). Shift tables will be constructed based on both the minimum and maximum post-baseline values for each subject. Data collected from unscheduled visits will be included in the determination of the per subject minimum and maximum values. A separate table will be provided which summarizes the results of the shift tables in which the number and

percentage of subjects with a shift to low (from normal, high, or unknown) and the number of subjects with a shift to high (from normal, low, or unknown) will be tabulated; percentages will be based on the number of subjects at risk. The number at risk for a shift to low (high) is the number of subjects whose baseline value was not low (high), including unknown, who had at least one post-baseline value. Only directions of change indicating a clinical concern will be included in this table summarizing the shifts. The direction of concern is provided in [Table 1](#).

Table 1: Direction of Change Indicating Clinical Concern for Laboratory Tests

Laboratory Test	Direction	Laboratory Test	Direction
Chemistry		Hematology	
Liver		White blood cells	Low and High
ALT/SGPT	High	Lymphocytes	Low and High
AST/SGOT	High	Neutrophils	Low and High
Total bilirubin	High	Monocytes	Low and High
GGT	High	Eosinophils	Low and High
Renal		Basophils	Low and High
Blood urea nitrogen	High	Red blood cells	Low and High
Creatinine	High	Hemoglobin	Low and High
Electrolytes		Hematocrit	Low and High
Sodium	Low and High	Platelets	Low and High
Potassium	Low and High		
Chloride	Low and High		
Other			
Glucose	Low and High		
Total protein	Low and High		

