14.2. Laboratory Safety Assessments

The following laboratory tests will be performed by the central laboratory to assess the safety profile of rFVIII Fc:

- Hematology: White blood cell count (WBC), differential, platelet count, hemoglobin, hematocrit
- Blood chemistry: sodium, potassium, chloride, glucose, total protein, total bilirubin, alanine aminotransferase (ALT), aspartate aminotransferase (AST), alkaline phosphatase (ALP), blood urea nitrogen (BUN), and serum creatinine
- Nijmegen-modified Bethesda assay for development of inhibitors

Refer to Section 4 for the timing of assessments.

CONFIDENTIAL

The information contained herein may not be used, disclosed, or published without the written consent of Biogen Idec MA Inc.

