8.3.1. Hematology and Chemistry

Hematology measurements that will be collected and listed include white blood cell count (WBC), differential, hemoglobin, hematocrit, and platelet count.

Chemistry measurements that will be collected and listed include electrolytes (sodium, potassium, chloride), glucose, total protein, total bilirubin, alanine aminotransferase (ALT), aspartate aminotransferase (AST), alkaline phosphatase (ALP) [collected for subjects from study 997HA301 only], blood urea nitrogen (BUN), and serum creatinine.

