8.3.1.3 Potentially Clinically Significant Laboratory Abnormalities

Abnormal laboratory values will also be evaluated by determining the number and percentage of subjects with at least one potentially clinically significant laboratory abnormality over the course of the study that also represents a worsening from baseline. The potentially clinically significant levels are based on Grade 2 or higher thresholds from the Common Toxicity Criteria for Adverse Events (CTCAE v 4.02 2009) where possible, or were defined by Bioverativ's Safety and Benefit Risk Management group. Subjects who have a post baseline laboratory value that meets the criteria for being potentially clinically significant but do not have a baseline value will be included in the numerator for determining the percentage of subjects with an abnormality. Percentages will be based on the number of subjects with at least one post baseline value for the given laboratory test. Threshold levels for potentially clinically significant laboratory abnormalities are provided in [Table 2](#) (hematology) and [Table 3](#) (chemistry). Data collected from unscheduled visits will be included in this analysis.

Table 2: Threshold Levels for Potentially Clinically Significant Hematology Abnormalities

Subjects from studies 997HA301/997HA307/997HA309		
	Low	High
White blood cells	$<3.0 \times 10^9/L$	$\geq 16 \times 10^9/L$
Lymphocytes	$<0.8 \times 10^9/L$	$>12 \times 10^9/L$
Neutrophils	$<1.5 \times 10^9/L$	$>13.5 \times 10^9/L$
Monocytes	NA	$>2.5 \times 10^9/L$
Eosinophils	NA	$>1.6 \times 10^9/L$
Basophils	NA	$>1.6 \times 10^9/L$
Hemoglobin	$\leq 115 \text{ g/L}$	$\geq 190 \text{ g/L}$
Hematocrit	$\leq 37\%$	$\geq 60\%$
Platelet count	$\leq 75 \times 10^9/L$	$\geq 700 \times 10^9/L$
Subjects from study 8HA02PED		
	Low	High
Neutrophils	$<1.5 \times 10^9/L$	NA
Eosinophils	NA	$>1.6 \times 10^9/L$
Hemoglobin	$<100 \text{ g/L}$	Increase in $>20 \text{ g/L}$ above ULN
Hematocrit	$<30\%$	$\geq 60\%$
Platelet count	$\leq 75 \times 10^9/L$	$\geq 700 \times 10^9/L$

NA = not applicable

Table 3: Threshold Levels for Potentially Clinically Significant Chemistry Abnormalities

Subjects from studies 997HA301/997HA307/997HA309		
	Low	High
Liver		
ALT/SGPT	NA	$\geq 3 \times \text{ULN}$
AST/SGOT	NA	$\geq 3 \times \text{ULN}$
Total bilirubin	NA	$\geq 34.2 \mu\text{mol/L}$
Renal		
Blood urea nitrogen	NA	$\geq 10.7 \text{ mmol/L}$
Creatinine	NA	$\geq 176.8 \mu\text{mol/L}$
Electrolytes		

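### SAP Table 1 puts GGT, which is not collected, into the laboratory shift summary and leaves out alkaline phosphatase, which is collected

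*SAP*

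**What the plan says.** **Collection.** Protocol 14.2 ends its chemistry list with "alkaline phosphatase (ALP), blood urea nitrogen (BUN), and serum creatinine". Footnote 8 to the screening and treatment schedule and footnote 3 to the surgery schedule (both Protocol Section 4) give the same tests. None of the three restricts ALP by parent study, and none mentions GGT. SAP 8.3.1 lists the same tests with one added limit: "alkaline phosphatase (ALP) [collected for subjects from study 997HA301 only], blood urea nitrogen (BUN), and serum creatinine". It does not mention GGT either.

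**Analysis.** SAP 8.3.1.2 has two layers. The first is the full shift tables: "Shift tables will be constructed based on both the minimum and maximum post-baseline values for each subject". The second is a separate table that condenses them into counts of subjects shifting to low or to high. For that second table, "Only directions of change indicating a clinical concern will be included in this table summarizing the shifts", and the directions are those in "Table 1: Direction of Change Indicating Clinical Concern for Laboratory Tests". The liver block there is ALT, AST, total bilirubin and GGT.

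SAP 8.3.1.3 counts potentially clinically significant abnormalities against Tables 2 and 3. The chemistry table, "Threshold Levels for Potentially Clinically Significant Chemistry Abnormalities", has ALT, AST and total bilirubin under liver for both subject groups. Neither ALP nor GGT has a threshold.

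**The concern.** Long-term safety is the primary objective of this extension study, and the shift summary and the abnormality table are where the SAP turns chemistry results into counts of subjects. A test with no entry in Table 1 has no direction of concern, so the condensed summary has no rule for counting it. A test with an entry but no planned collection gives an empty row.

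A programmer working from this SAP meets both problems: a GGT row with nothing to put in it, and an ALP variable with no rule. Any choice then made at programming time would be made after the data exist. ALT, AST and bilirubin each have both a direction and a threshold. ALP has neither, and the SAP gives no reason for treating it differently.

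**Working it through.** The plan states no figure to reproduce on this point. The check is a comparison of lists.

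| Source | Chemistry tests | ALP | GGT |
|---|---|---|---|
| Protocol Section 4, screening/treatment footnote 8 | 11 | yes, unrestricted | no |
| Protocol Section 4, surgery footnote 3 | 11 | yes, unrestricted | no |
| Protocol 14.2 | 11 | yes, unrestricted | no |
| SAP 8.3.1 | 11 | yes, 997HA301 subjects only | no |
| SAP Table 1 (directions of concern) | 11 | no | yes, High |
| SAP Table 3, subjects from 997HA301/307/309 | 10 | no | no |
| SAP Table 3, subjects from 8HA02PED | 7 | no | no |

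1. **Collected tests against Table 1.** The 11 collected tests are sodium, potassium, chloride, glucose, total protein, total bilirubin, ALT, AST, ALP, BUN and creatinine. Table 1 also has 11, and 10 are common to both. Collected but not in Table 1: 11 − 10 = 1, which is ALP. In Table 1 but not collected: 11 − 10 = 1, which is GGT.

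2. **Is GGT another label for ALP?** No. The SAP's abbreviation list defines the two separately.

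3. **Collected tests against Table 3.** For subjects from 997HA301/307/309, 11 − 10 = 1 collected test has no threshold: ALP. For 8HA02PED subjects, 11 − 7 = 4 have none: ALP, BUN, sodium and potassium. ALP is therefore in none of the three chemistry lists (Table 1 and the two halves of Table 3) that drive the shift summary and the abnormality counts.

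4. **What ALP keeps.** SAP 8.3.1.1 summarizes chemistry results and change from baseline descriptively, with no test excluded. SAP 8.3 puts all laboratory data in listings and marks values outside the normal range. The sentence that sets up the full shift tables is not limited to Table 1 tests. However, SAP 8.3 orders all laboratory summaries by the tables in Section 8.3.1, where ALP has no position. Its place in the full shift tables is thus neither excluded nor specified.

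5. **Reach of the 997HA301 limit.** Planned numbers (SAP 3.3.1) are 144 from 997HA301, 50 from 8HA02PED, 12 from 997HA307 and 8 from 997HA309. Total: 144 + 50 + 12 + 8 = 214. Outside 997HA301: 50 + 12 + 8 = 70, and 70/214 = 32.7%. This is an upper bound, reached only if ALP was in fact measured in all of them.

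The hematology lists show a smaller mismatch of the same kind: Table 1 has a row for red blood cells, which none of the four collection lists names.

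**The case against.** Much of the opposing case stands, and it limits the point.

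**A reader might infer that an ALP rise cannot appear in any incidence table.** The documents do not support that. The full minimum/maximum shift tables are not confined to Table 1 tests, and the SAP's list of tables treats the full and condensed chemistry outputs as separate items. Protocol 15.1.2 also allows an abnormal laboratory finding to be an adverse event, in which case it would enter the treatment-emergent tables.

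**A reader might infer that the 997HA301 limit is an error to be struck out.** It conflicts with the protocol's unrestricted lists, but that does not make it wrong. Footnote 2 to the schedule and the opening of Protocol Section 14 confine future enrollees to the assessments of their parent study. This SAP serves the final study report, so the note may simply record what happened. The documents do not say which chemistry tests each parent study ran, or which parent studies that restriction covers.

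**A reader might infer that ALP results from the other parent studies will be dropped altogether.** If they were never collected, nothing is lost. If they were, the listings and the descriptive summaries cover them.

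**The missing Table 3 threshold is weak evidence on its own.** The SAP sets thresholds for selected tests only, as the 8HA02PED list shows, so an ALP threshold is a matter of choice.

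None of this answers the Table 1 mismatch. Even if the 997HA301 limit is right, ALP is collected in the largest planned group (144 subjects) and has no direction of concern, while a test that no list collects has one.

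**Conclusion.** The point holds for Table 1 and is minor. The condensed shift summary, as specified, has a row for a test with no planned data and no count for one of the 11 collected chemistry tests, which is one of four liver tests if ALP is grouped with ALT, AST and bilirubin. ALP is also absent from the clinically significant abnormality table. The gap is in these categorical summaries. Inhibitor development, the primary endpoint, is unaffected.

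The conclusion assumes that the collection lists, which agree with one another on ALP and GGT, are complete. The pattern looks like one test standing where the other should be, but the documents do not establish the cause. Whether the 997HA301 limit is correct cannot be settled from the documents.

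**What to change.** 1. **SAP Table 1:** replace GGT with ALP, direction High. State that ALP is included in the full shift tables and the condensed summary for every subject with central-laboratory ALP data.
2. **SAP 8.3.1:** check the 997HA301 limit against the collected data and reconcile it with Protocol 14.2 and schedule footnote 8. If it is wrong, remove it. If it is right, keep it, give the reason and state the ALP denominator.
3. **Optional, SAP Table 3:** have the sponsor's safety group set an ALP threshold by the route 8.3.1.3 already describes, namely the toxicity-grade thresholds where possible and the group's own definition otherwise.
4. **In the same edit:** reconcile the red blood cell row in Table 1 with the hematology collection lists.

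The cost is a few lines of SAP text and table entries plus one query of the laboratory data. No new assessments are needed.

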8.3.1.3 Potentially Clinically Significant Laboratory Abnormalities

Abnormal laboratory values will also be evaluated by determining the number and percentage of subjects with at least one potentially clinically significant laboratory abnormality over the course of the study that also represents a worsening from baseline. The potentially clinically significant levels are based on Grade 2 or higher thresholds from the Common Toxicity Criteria for Adverse Events (CTCAE v 4.02 2009) where possible, or were defined by Bioverativ's Safety and Benefit Risk Management group. Subjects who have a post baseline laboratory value that meets the criteria for being potentially clinically significant but do not have a baseline value will be included in the numerator for determining the percentage of subjects with an abnormality. Percentages will be based on the number of subjects with at least one post baseline value for the given laboratory test. Threshold levels for potentially clinically significant laboratory abnormalities are provided in [Table 2](#) (hematology) and [Table 3](#) (chemistry). Data collected from unscheduled visits will be included in this analysis.

Table 2: Threshold Levels for Potentially Clinically Significant Hematology Abnormalities

Subjects from studies 997HA301/997HA307/997HA309		
	Low	High
White blood cells	$<3.0 \times 10^9/L$	$\geq 16 \times 10^9/L$
Lymphocytes	$<0.8 \times 10^9/L$	$>12 \times 10^9/L$
Neutrophils	$<1.5 \times 10^9/L$	$>13.5 \times 10^9/L$
Monocytes	NA	$>2.5 \times 10^9/L$
Eosinophils	NA	$>1.6 \times 10^9/L$
Basophils	NA	$>1.6 \times 10^9/L$
Hemoglobin	$\leq 115 \text{ g/L}$	$\geq 190 \text{ g/L}$
Hematocrit	$\leq 37\%$	$\geq 60\%$
Platelet count	$\leq 75 \times 10^9/L$	$\geq 700 \times 10^9/L$
Subjects from study 8HA02PED		
	Low	High
Neutrophils	$<1.5 \times 10^9/L$	NA
Eosinophils	NA	$>1.6 \times 10^9/L$
Hemoglobin	$<100 \text{ g/L}$	Increase in $>20 \text{ g/L}$ above ULN
Hematocrit	$<30\%$	$\geq 60\%$
Platelet count	$\leq 75 \times 10^9/L$	$\geq 700 \times 10^9/L$

NA = not applicable

Table 3: Threshold Levels for Potentially Clinically Significant Chemistry Abnormalities

Subjects from studies 997HA301/997HA307/997HA309		
	Low	High
Liver		
ALT/SGPT	NA	$\geq 3 \times \text{ULN}$
AST/SGOT	NA	$\geq 3 \times \text{ULN}$
Total bilirubin	NA	$\geq 34.2 \mu\text{mol/L}$
Renal		
Blood urea nitrogen	NA	$\geq 10.7 \text{ mmol/L}$
Creatinine	NA	$\geq 176.8 \mu\text{mol/L}$
Electrolytes		
Sodium	$\leq 126 \text{ mmol/L}$	$\geq 156 \text{ mmol/L}$
Potassium	$\leq 3 \text{ mmol/L}$	$\geq 6 \text{ mmol/L}$
Chloride	$\leq 90 \text{ mmol/L}$	$\geq 118 \text{ mmol/L}$
Other		
Glucose	$\leq 2.22 \text{ mmol/L}$	$\geq 9.71 \text{ mmol/L}$
Total protein	$\leq 45 \text{ g/L}$	$\geq 100 \text{ g/L}$
Subjects from study 8HA02PED		
	Low	High
Liver		
ALT/SGPT	NA	$>3 \times \text{ULN}$

AST/SGOT	NA	>3 × ULN
Total bilirubin	NA	>1.5 × ULN
Renal		
Creatinine	NA	>1.5 × ULN
Electrolytes		
Chloride	≤90 mmol/L	≥118 mmol/L
Other		
Glucose	<3.1 mmol/L	>8.9 mmol/L
Total protein	≤45 g/L	≥100 g/L

NA = not applicable, ULN = upper limit of normal

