3. STUDY DESIGN

3.1. Overall Study Design and Plan

This is an open-label, multi-center, long-term study of IV administration of rFVIII Fc in previously treated patients (PTPs) with hemophilia A who have completed the A-LONG study (997HA301), the pediatric study (8HA02PED), or any other study with rFVIII Fc that plans to enroll subjects into this study after study completion or at a time specified in the protocol. This is a global study and will be offered to those countries participating in the parent studies.

Based on final and estimated sample sizes from these studies, approximately 214 subjects from studies 997HA301, 8HA02PED, 997HA307, and 997HA309 may be eligible to enroll in this extension study. The End of Treatment (EOT) Visit of the previous study may serve as the initial visit of the extension study. Assessments performed at this visit will be used to confirm eligibility for participation in the extension study.

Study visits are scheduled at 6-month (± 2 weeks) intervals following completion of Visit 1. Unscheduled visits may occur as deemed necessary by the Investigator. For subjects who undergo surgery, the Last Post-Operative Visit assessments will be performed when the subjects switch from their post-surgery dosing regimen to a regimen outlined in Section 3.2.1.

For subjects undergoing surgery, post-operative clinic visits may be more frequent. For subjects undergoing major surgery, a visit (Visit 3) is required 1-2 weeks after surgery (not required for minor surgery). A last post-operative visit (Visit 4) is required only if subjects who had major surgery did not return to a regular rFVIII Fc regimen as determined by the Investigator at Visit 3.

All subjects will have the opportunity to continue in this study for up to 4 years or until rFVIII Fc is commercially available in the applicable participating country.

Subjects first dosed with rFVIII Fc when <12 years of age in the parent study will be followed to at least 100 EDs in total across parent and extension study, even if rFVIII Fc becomes commercially available.

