3.3. Number of Subjects

3.3.1. Sample Size

As this is an extension study, the sample size was based on the planned sample sizes of studies 997HA301 (N=144), 8HA02PED (N=50), 997HA307 (N=12), and 997HA309 (N=8, the subset of subjects from Australia and New Zealand only). This might be increased based upon enrollment being greater than expected in these studies.

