8. SAFETY ANALYSIS

Safety data will be summarized for subjects from the parent study or subjects from the parent studies combined along with the overall total. The analysis population for safety analyses is defined in Section 4.3.

Adverse events (AEs) will be summarized for subjects from each parent study and overall for all subjects in study 8HA01EXT, regardless of treatment arm for subjects from studies 997HA301, 997HA307, and 997HA309, age cohort for subjects from study 8HA02PED, and treatment regimen in study 8HA01EXT.

In addition, all data from study 8HA01EXT will be provided in data listings.

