Subjects from study 8HA02PED: Summary of annualized bleeding rate by location and type of bleeds

Subjects from study 8HA02PED: Summary of annualized bleeding rate by the presence of target joints at screening in parent study

Subjects from study 8HA02PED: Summary of annualized bleeding rate by ePD entry compliance
Summary of subject's assessment of response to rFVIII Fc injections for the treatment of bleeding episodes

Summary of number of injections required for resolution of a bleeding episode

Summary of dose (IU/kg) of rFVIII Fc for resolution of bleeds

Summary of results and change from study 8HA01EXT baseline: CHO-KLAT total score from the Child Self-report Questionnaire

Summary of results and change from study 8HA01EXT baseline: CHO-KLAT total score from the Parent/Proxy Questionnaire

Summary of results and change from study 8HA01EXT baseline: Hemo-Sat total score and subscores

Summary of EQ-5D-Y descriptive system

Summary of results and change from study 8HA01EXT baseline: EQ-5D-Y visual analogue scale

Summary of hemophilia-related health-economic parameters

Summary of health economic parameters for all physician and emergency room visits

Summary of results and changes from study 8HA01EXT: Hemophilia Joint Health Score (HJHS)

Overall groups of subjects in 8HA01EXT (as described in Section 5.1):

Summary of compliance for the treatment of bleeding episodes

Summary of prophylactic dose compliance

Summary of prophylactic dosing interval compliance

Summary of prophylactic compliance

Summary of EPD entry compliance

Overall summary of rFVIII Fc treatment-emergent adverse events

Summary of rFVIII Fc treatment-emergent adverse events by preferred term in descending order of incidence

Summary of rFVIII Fc treatment-emergent adverse events by relationship to treatment

Summary of rFVIII Fc treatment-emergent serious adverse events

Summary of anti-rFIIIV Fc antibodies

Surgery subgroup – Summary of Investigators'/Surgeons' assessment of subjects' hemostatic response to rFVIII Fc post major surgery

Surgery subgroup – Number of injections and dose required to maintain hemostasis during major surgery

Surgery subgroup - Estimated total blood loss during major surgery

Surgery subgroup – Total rFVIII Fc consumption (IU/kg) per major surgery

Surgery subgroup - summary of number of bleeds after surgery per major surgery

Summary of Investigators'/Surgeons' assessment of subjects' hemostatic response to rFVIII Fc post minor surgery

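### For seven laboratory tests, and for high neutrophils, SAP 8.3.1.3 counts 8HA02PED subjects in the overall denominator although no threshold exists by which they could enter the numerator

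*SAP*

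**What the plan says.** SAP Section 8.3.1.3 counts subjects who have at least one potentially clinically significant value that is also worse than baseline. The base is: "Percentages will be based on the number of subjects with at least one post baseline value for the given laboratory test". Nothing in that rule requires that a threshold exist for the subject.

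Tables 2 and 3 set the thresholds in two blocks, headed "Subjects from studies 997HA301/997HA307/997HA309" and "Subjects from study 8HA02PED". The second block is shorter, and some of its cut-offs differ.

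On columns, SAP Section 8 says: "Safety data will be summarized for subjects from the parent study or subjects from the parent studies combined along with the overall total". The table in Section 5.1 likewise has an overall group for safety. In the List of Tables, the hematology and chemistry summaries of these abnormalities stand under the heading for overall groups in 8HA01EXT.

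On collection, SAP Section 8.3.1 restricts one test, alkaline phosphatase, to subjects from 997HA301. White cells with differential, blood urea nitrogen, sodium and potassium carry no such restriction. Table 1 in Section 8.3.1.2 includes all seven tests among those that go into the shift summary, again without separating parent studies.

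**The concern.** A percentage is interpretable only if everyone in the denominator could have been counted in the numerator. For the tests that lack a pediatric threshold, the stated base breaks this condition in the pooled column: a child with any sodium value adds one to the denominator and cannot be a case.

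The error has a known direction. The overall figure can only be too low relative to the rate among subjects who could be evaluated, and it gets lower as more children contribute results. A reader who takes the overall column as the study's summary would see a lower rate of these abnormalities than was found in the subjects examined for them. Long-term safety is the primary objective, although the primary endpoint is inhibitor development, which this point does not touch.

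Elsewhere the SAP chooses its base with more care. Shift percentages use subjects at risk (Section 8.3.1.2), and antibody percentages use subjects who were negative beforehand and were evaluated afterwards (Section 8.3.3). Section 8.3.1.3 has no matching restriction.

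**Working it through.** **Step 1. Which tests lack a pediatric threshold (SAP Tables 2 and 3).**

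- 997HA301/307/309: 9 hematology + 10 chemistry = 19 tests.
- 8HA02PED: 5 hematology + 7 chemistry = 12 tests.
- Difference: 19 − 12 = 7, namely white blood cells, lymphocytes, monocytes, basophils, blood urea nitrogen, sodium and potassium.
- High neutrophils is marked NA for 8HA02PED; low neutrophils does have a threshold.

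By test and direction, white cells, lymphocytes, sodium and potassium have two thresholds each for older subjects (4 × 2 = 8). Monocytes, basophils and blood urea nitrogen have one each (3). High neutrophils adds 1. So 8 + 3 + 1 = 12 test-directions are affected.

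**Step 2. Planned numbers.** SAP Section 3.3.1 gives 144 + 50 + 12 + 8 = 214, which reproduces the total in Section 3.1 ("approximately 214 subjects from studies 997HA301, 8HA02PED, 997HA307, and 997HA309 may be eligible"). Of these, 50 come from 8HA02PED and 144 + 12 + 8 = 164 from the other studies.

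**Step 3. Size of the dilution.** Let x be the cases among n_A older subjects, and let n_P children have a value.

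- Rate among evaluated subjects: x / n_A.
- Overall percentage under the stated rule: x / (n_A + n_P).
- Ratio: n_A / (n_A + n_P). Relative shortfall: n_P / (n_A + n_P).

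| Assumption | n_A | n_P | Shortfall |
|---|---|---|---|
| SAP planned numbers, all children have values | 164 | 50 | 50/214 = 23.4% |
| Protocol Section 16.10 numbers (144 + 50) | 144 | 50 | 50/194 = 25.8% |
| All 164 subjects dosed in 997HA301 enrol (Protocol Section 5.1.3), plus 12 + 8 | 184 | 50 | 50/234 = 21.4% |
| SAP numbers, 40 children have values | 164 | 40 | 40/204 = 19.6% |
| SAP numbers, 25 children have values | 164 | 25 | 25/189 = 13.2% |
| SAP numbers, no children have values | 164 | 0 | 0% |

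That 164 is both the planned total for the three older-subject studies and the number dosed in 997HA301 is a coincidence.

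**Step 4. In percentage points (planned numbers, illustrative case counts).**

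- 2 cases: 2/164 = 1.22% becomes 2/214 = 0.93%.
- 8 cases: 8/164 = 4.88% becomes 8/214 = 3.74%.
- 16 cases: 16/164 = 9.76% becomes 16/214 = 7.48%.

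**Step 5. Against the pooled incidence that would be seen if children were evaluated too.** This depends on an unknown pediatric rate. Let it be c times the rate in older subjects, with 8 cases among the latter. The pooled incidence is (8 + 50 × c × 8/164)/214, to be compared with the reported 3.74%.

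- c = 0: 3.74%, no understatement.
- c = 0.5: 4.31%, understated by 13.2%.
- c = 1: 4.88%, understated by 23.4%.
- c = 2: 6.02%, understated by 37.9%.

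**The case against.** The strongest reply is that little depends on this column. Section 5.1 separates the parent-study groups because their safety profiles may differ, and the columns for 997HA301 and for 997HA301/307/309 combined are not diluted. Twelve of the 19 tests have pediatric thresholds. The shorter pediatric list also looks deliberate: it has its own cut-offs, and Section 8.3.1.3 attributes the levels to toxicity criteria or to the sponsor's safety group. All of this stands and limits the scope. It does not answer the denominator rule, which is wrong for the overall column whether or not the list is deliberate.

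A second reply is that children may not have these values, in which case the stated base already leaves them out. The protocol's list of laboratory tests does not settle this, since it also includes alkaline phosphatase without restriction, which the SAP then confines to 997HA301. But the SAP restricts only that test, so pediatric values for the seven are likely. Their number per test is not given, and the size must stay conditional on it.

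Two stronger readings are tempting and are not supported.

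- A reader might infer that abnormal sodium, potassium, blood urea nitrogen or white-cell values in children go unexamined. They do not. The seven tests go through the shift tables on each subject's minimum and maximum, unscheduled visits included. All laboratory data are listed with abnormal values identified, and separate listings by normal range are planned. Within white cells, low neutrophils and high eosinophils do have pediatric thresholds.
- A reader might infer that the pediatric column will print 0/50 and might attach an exact upper limit (7.1%) to it. The SAP does not say how such a cell is displayed, the table shells are not among the documents, and Tables 2 and 3 already use NA. No interval is planned for laboratory abnormalities; the exact interval in Protocol Section 16.7.2 concerns inhibitors.

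**Conclusion.** The concern holds in a narrow form. Taken as written, the base in SAP Section 8.3.1.3 makes the overall percentage too low, relative to the rate among evaluable subjects, for white blood cells, lymphocytes, monocytes, basophils, blood urea nitrogen, sodium and potassium, and for high neutrophils. It affects no other test and no other column.

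At the SAP's planned numbers, and if all 50 children have a post-baseline value, the shortfall is about 23% in relative terms. Over the enrolment figures in the documents it is 21% to 26%; the lower end assumes that every subject dosed in 997HA301 enrolled. It shrinks to 13% to 20% with 25 to 40 children contributing, and vanishes with none. In percentage points it is small when the abnormality is rare: 0.3 points at 2 cases and 1.1 at 8.

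It does not follow that overall laboratory incidences in general are understated, nor that the true pooled incidence is missed by 23%. The latter depends on a pediatric rate that the documents do not give.

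**What to change.** Add to SAP Section 8.3.1.3 that, for each test and direction, the denominator is the number of subjects with a post-baseline value whose parent-study group has a threshold in Table 2 or 3. State that where 8HA02PED has none its cell is shown as not applicable or not evaluated, and that the overall column then rests on the evaluated groups only, with a footnote naming them. With 8 cases at planned numbers, the overall entry would read 8/164 = 4.88% instead of 8/214 = 3.74%.

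Whether children should have thresholds for these tests is for the sponsor's safety group. If it adds any, this should be done before database lock, and the same rule then includes the children without further change.

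The cost is one sentence, one footnote and a denominator flag in the program; no new data are needed. The drawback is that denominators in the overall column will differ between rows, so each row should print its own n.
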